1.1 Study Design

This is a multi-center, open label, phase II study evaluating infigratinib anti-tumor activity in advanced or metastatic cholangiocarcinoma patients with FGFR genetic alterations. All patients will receive infigratinib once daily on a three week on (21 days), 1 week off (7 days) schedule in 28-day cycles. Approximately 120 patients in total will be enrolled into Cohort 1 on the study. As of Amendment 2, only patients with advanced or metastatic cholangiocarcinoma with FGFR gene fusions/translocation will be enrolled into Cohort 1. As of Amendment 4, two new cohorts, Cohort 2 and Cohort 3, were added to this study. Cohort 2 is planned to enroll approximately 20 patients with FGFR genetic alterations other than FGFR2 gene fusions or translocations and Cohort 3 is planned to enroll up to approximately 20 patients with FGFR2 gene fusions or translocations who have received a prior FGFR inhibitor other than infigratinib. According to Amendment 2, the final market image version 3 (FMI III) formulation of infigratinib replaced FMI I. According to amendment 4, the final market image version 4 (FMI IV) formulation of infigratinib will be used for patients in Cohort 2 and 3. Patients who started treatment prior to the implementation of amendment 2 should continue to receive the formulation of infigratinib that they received at the initiation of treatment until FMI IV is available at the study site. Pharmacokinetics, safety, and tolerability data from all available patients enrolled in either Cohort 2 or Cohort 3 treated with FMI IV up to the end of cycle 1 of treatment will be assessed and compared with the historical data from patients treated with FMI III.

In order to assess the antitumor activity of infigratinib, patients in all cohorts will be evaluated for tumor response radiographically every 8 weeks until disease progression or discontinuation from study using RECIST 1.1 criteria.

Figure 1: Study Design (Applied to Protocol Version 6 (Amendment 5))

^a Screening assessments are to be completed within 21 days prior to the first dose of treatment, except for the radiological tumor assessment, which can be performed within 28 days prior to the first dose.

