2 STATISTICAL METHODS

2.1 Data Analysis General Information

Study data will be analyzed by QED Therapeutics and/or designated CRO(s) using the most updated SAS® version in the statistical computing environment. PK parameters will be calculated using non-compartmental methods available in Phoenix WinNonlin version 7.0 or higher.

Two formal interim analyses for Cohort 1 are planned after Amendment 3 as described in Section 2.9. The first formal interim analysis will include all patients in Cohort 1 who receive study treatment before the interim analysis cutoff date. The efficacy analysis for the first formal interim analysis for Cohort 1 will be focused on the population as described in Section 2.2.2 below. The second formal interim analysis will be conducted on all the subjects with FGFR2 fusions or translocations in Cohort 1. The primary analysis for Cohort 1 will be conducted when all patients in Cohort 1 have the potential to be followed for at least 10 months after their initial exposure to study treatment. For the interim and primary analyses for Cohort 1, patients will be grouped by fusion status (if subjects without FGFR2 fusions or translocations are included) and formulation. Here, the formulation refers to the first formulation a subject received if a subject switched formulation during the study as described in Section 1.1.

For Cohorts 2 and 3, review of data will be performed after a total of 15 patients in either Cohort 2 or 3 have been treated with FMI IV for at least one cycle. Primary analysis will be conducted when all patients in the cohorts have the potential to be followed for at least 10 months after their initial exposure to study treatment. Additionally, for Cohort 3, one interim analysis will be conducted after the first 10 dosed patients in this cohort have the potential to complete their second scheduled scans (approximately 16 weeks from their first dose) to determine if the cohort will be expanded.

The additional data for patients continuing to receive study treatment or remain in study past the data cutoff date of the primary analysis, as allowed by the protocol, will be reported in a final CSR that will be prepared at the end of the study. In the final CSR, analyses will be done for each cohort, for patients enrolled in Cohort 1 who do not have FGFR2 fusions or translocations, data may be combined and summarized with Cohort 2.

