2.1.1 General Definitions

2.1.1.1 Investigational Drug and Study Treatment

Investigational drug will refer to infirgratinib as an oral formulation. The terms investigational drug and study drug/treatment are used interchangeably. For consistency across studies, the term study treatment will be used throughout this document.

Table 3: Dose and Treatment Schedule

| Study treatment | Formulation | Pharmaceutical form and route of administration | Dose | Frequency and/or Regimen |
|-----------------|-------------|---|---|--|
| infirgratinib | FMI I | Capsule(s) for oral use | 125 mg (administered as one 100 mg capsule and one 25 mg capsule) | Daily (3 weeks on, 1 week off schedule in 28-day cycles) |
| | FMI III | | | |
| | FMI IV | | | |

A **treatment** is defined by the dose formulation (FMI I, FMI III and FMI IV). The treatment formulation is determined by the formulation a subject first received if a subject switches formulation during the study as described in Section 1.1.

Unless otherwise specified, all efficacy related analyses will be done separately for all patients, patients with baseline FGFR2 gene fusion/translocation, and patients with other FGFR genomic

alterations if subjects without FGFR2 fusion/translocation are included in the analysis. In addition, within patients who had baseline FGFR2 gene fusion/translocation, the data will be summarized by treatment. Unless otherwise specified, for all other analyses, including safety, disposition, demographic/baseline disease characteristics, study drug exposure and prior/concomitant/post therapy related analyses, will be done separately for all subjects, all subjects by FGFR status (FGFR2 gene fusion/translocation vs. other FGFR genomic alterations) if subjects without FGFR2 fusion/translocation are included in the analysis, and all subjects by treatment.

Note that reporting by treatment is equivalent to reporting by formulation, and “by treatment” will be used throughout this document.

2.1.1.2 *Date of First/Last Administration of Study Treatment*

In the single agent arm, the date of first (last) administration of study treatment is derived as the first (last) date when a non-zero dose of infigratinib was administered and recorded on the Dosage Administration Record (DAR) eCRF. If a subject has not ended treatment at data cut-off date for an analysis, the subject is considered ongoing at the last dosing record.

2.1.1.3 *Study Day*

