Unless otherwise specified, all the analyses will be conducted on FAS. All efficacy related analyses will be done separately for all subjects, subjects with baseline FGFR2 gene fusions or translocations and subjects with only other FGFR genomic alterations. In addition, for subjects with baseline FGFR2 gene fusions or translocations, the data will be summarized by treatment (formulation FMI I vs FMI III vs FMI IV). The analyses, including safety, disposition, demographic/baseline disease characteristics, study drug exposure and prior/concomitant/post therapy related analyses, will be done separately for all subjects, all subjects by FGFR status (FGFR2 gene fusion/translocation vs. only other FGFR genomic alterations) and all subjects by treatment.

Unless otherwise specified, the FAS will be used for all listings of raw data.

2.2.2 Interim Efficacy Analysis Set 1 for Cohort 1

The Interim Efficacy Analysis Set 1 for Cohort 1 includes all subjects with planned extensive PK sample collection in Cohort 1 (regardless of whether extensive PK samples were actually collected) and all patients enrolled prior to Amendment 2. Unless otherwise specified, the Interim Efficacy Analysis Set 1 will be used as the primary efficacy analysis set for the first formal interim analysis for Cohort 1 after Amendment 3. Patients will be classified according to their baseline genetic status (FGFR2 gene fusions or translocations vs only other FGFR genetic alterations).

2.2.3 Interim Analysis Set 2 for Cohort 1

The Interim Analysis Set 2 for Cohort 1 includes patients in Cohort 1 with FGFR2 gene fusions or translocations who have received at least one dose of infiratinib. Interim Analysis Set 2 for Cohort 1 will be used as the primary analysis set for the second formal interim analysis for Cohort 1 after Amendment 3.

2.2.4 Sensitivity Analysis Set for Cohort 1

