2.7.2.1.2 Data Analysis

AE Summaries

AE summaries will include all AEs occurring during on-treatment period, i.e. treatment emergent AEs. Treatment emergent AEs (TEAEs) include all AEs that started on or after the first administration day of study treatment and up to last study administration day of study treatment +30 days. All AEs collected in the AE (e)CRF page will be listed along with the information collected on those AEs, eg, AE relationship to study drug, AE outcome, etc. Treatment-emergent AEs will be flagged in the listings.

TEAEs will be summarized by number and percentage of subjects having at least one TEAE, having at least one TEAE in each primary system organ class (SOC) and for each preferred term (PT) using MedDRA coding. A subject with multiple occurrences of an AE will be counted only once in the respective AE category. A subject with multiple CTCAE grades for the same preferred term will be summarized under the maximum CTCAE grade recorded for the event. AE with missing CTCAE grade will be included in the 'All grades' column of the summary tables.

In TEAE summaries the primary system organ class will be presented alphabetically, and the preferred terms will be sorted within primary SOC in descending frequency. The sort order for the preferred term will be based on their frequency in FAS. The following TEAE summaries will be produced by treatment and by FGFR2 fusion/translocation status:

- Overview of TEAEs and deaths (number and % of subjects who died from fatal TEAE, number and % of subjects with any TEAE, any treatment emergent serious AE, any TEAE leading to dose reductions/interruptions, TEAE leading to discontinuation of study treatment)
- All TEAEs by SOC and PT and worst grade
- Treatment related TEAEs by SOC and PT and worst grade
- Grade 3 or 4 TEAEs by SOC and PT and worst grade
- Treatment emergent serious AEs (SAEs) by SOC and PT and worst grade
- Treatment emergent serious treatment-related AEs by SOC and PT and worst grade
- TEAE with fatal outcome by SOC and PT and worst grade
- TEAE leading to study treatment discontinuation by SOC, PT and grade
- TEAE leading to dose interruption/adjustment by SOC, PT and grade
- TEAE leading to treatment discontinuation by SOC and PT and worst grade
- TEAE requiring additional medication or therapies by SOC and PT and worst grade
- All TEAEs by PT by descending order of frequency
- Treatment related TEAEs by PT by descending order of frequency

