2.9 Interim Analysis

Safety and efficacy data will be continuously monitored by QED Therapeutics in conjunction with the investigators for decision-making purposes.

For Cohort 1, one analysis was performed before Amendment 2 based on the 61 patients enrolled in the study (30 Jun 2016). Protocol amendment 2 restricted enrollment to patients with FGFR2 fusions or translocations, and the formulation was changed from FMI I to FMI III.

After 20 subjects had been treated with FMI III (for at least one cycle) based on Amendment 2, a comprehensive review of all relevant data such as PK, safety, dose interruptions/reductions, and available efficacy was performed. PK, safety, and tolerability data from the first 20 subjects treated with FMI III up to the end of cycle 1 of treatment were assessed and compared with the historical data from subjects treated with FMI I. Upon review of the data, it was decided to continue dosing all subsequent patients treated with FMI III at 125 mg on a 3 weeks on, 1 week off schedule.

In addition, two formal interim analyses for Cohort 1 are planned after Amendment 3:

- The first formal interim analysis for Cohort 1 was conducted when all patients in the Interim Efficacy Analysis Set 1 have been followed for at least 10 months after their initial exposure to the study treatment. This interim analysis will be done using only patients in Cohort 1. Efficacy analysis for this interim analysis will be based on the Interim Efficacy Analysis Set 1 and some key efficacy analyses may be repeated in the FAS. All the other analyses will be conducted on FAS unless otherwise specified.
- The second will be conducted when all the patients who received infiratinib at the time of the first formal interim analysis have at least 10 months follow-up after their initial exposure to infiratinib.

Additionally, for Cohorts 2 and 3, review of data will be performed after a total of 15 patients in either Cohort 2 or 3 have been treated with FMI IV for at least one cycle. A formal interim analysis will be conducted for Cohort 3 when the first dosed 10 patients in Cohort 3 have the potential to complete the second scheduled scan. This interim analysis will only include data from Cohort 3. This is to determine if an additional 10 patients will be added to Cohort 3.

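### Cohort 1 adverse-event tables by first formulation give crude percentages over unequal potential follow-up, with no common-window or exposure-adjusted summary for later toxicity

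*SAP*

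**What the plan says.** - **Measure.** SAP 2.7.2.1.2: "TEAEs will be summarized by number and percentage of subjects having at least one TEAE". The AESI tables in the same section also give the number and percentage of patients with at least one event.
- **Window.** An event counts if it starts on or after the first dose and "up to last study administration day of study treatment +30 days".
- **Grouping.** "The following TEAE summaries will be produced by treatment and by FGFR2 fusion/translocation status". SAP 2.1.1.1 equates treatment with formulation and adds: "The treatment formulation is determined by the formulation a subject first received if a subject switches formulation during the study". SAP 2.2.1 runs analyses separately by cohort.
- **Switching.** Under SAP 1.1, patients who started before Amendment 2 "continue to receive the formulation of infigratinib that they received at the initiation of treatment until FMI IV is available". Protocol 6.5 also moves FMI III patients to FMI IV.
- **Follow-up.** SAP 2.1 times the Cohort 1 primary analysis for when all patients "have the potential to be followed for at least 10 months after their initial exposure to study treatment". At the second interim, safety uses Interim Analysis Set 2 (SAP 2.7.2), which SAP 2.2.3 defines as "patients in Cohort 1 with FGFR2 gene fusions or translocations who have received at least one dose of infiratinib". The 10-month minimum there covers only patients already dosed at the first interim (SAP 2.9).
- **Exposure.** Duration of exposure is summarised on its own (SAP 2.5.1). It is never a denominator for adverse events, and no time-to-onset, cumulative-incidence or common-window TEAE table is listed.

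**The concern.** A crude percentage depends on how long patients are observed as well as on how often events occur. Formulation in Cohort 1 follows calendar time, so the two groups can be observed for different lengths even if the capsules are equally safe. A table that puts the percentages side by side invites a comparison they cannot support.

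FMI I against FMI III is the contrast of interest, because Protocol 2.3 reports exposure about 21-35% higher with FMI III on cross-study comparison. Several AESIs (tissue and vascular calcification, eye disorders) could plausibly accrue with time on drug, and these later events are the ones most affected by unequal observation.

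**Working it through.** The documents give no follow-up, exposure or event rate by formulation, so there is no planned figure to reproduce. The check has two parts: calendar dates, then a simple model.

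**1. Potential follow-up from dates in the documents**
- 61 patients were enrolled by 30 Jun 2016 (SAP 2.9). To Amendment 5 (15 Jan 2020) is 1,294 days, or 42.5 months.
- FMI III began with Amendment 2 (24 Jan 2017). To 15 Jan 2020 is 1,086 days, or 35.7 months, for the earliest possible FMI III start.
- The floor at the primary analysis is 10 months.

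The ranges overlap: early FMI III patients may have about 3 years.

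**2. Model**
- Time on treatment is exponential with rate μ = ln 2 / 175 = 0.00396 per day. The 175-day median PFS (95% CI 130-230) in the Amendment 2 rationale stands in for time on treatment; this is an assumption.
- The event window is the smaller of (time on treatment + 30 days) and potential follow-up F. The 30 days is the SAP's figure; Protocol 10.5.2.1 has 90.
- The event hazard is the same constant for both formulations. For an illustrative 10% risk per 6 months, λ = -ln 0.9 / 182.6 = 0.000577 per day.

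Crude incidence = 1 - exp(-30λ) + exp(-30λ) × λ/(λ+μ) × [1 - exp(-(λ+μ)(F-30))], where 1 - exp(-30λ) = 0.0172, exp(-30λ) = 0.9828 and λ/(λ+μ) = 0.1271.

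- F = 42 months (1,278 days): 0.0172 + 0.9828 × 0.1271 × 0.9965 = **14.2%**
- F = 10 months (304 days): 0.0172 + 0.9828 × 0.1271 × 0.7121 = **10.6%**

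Mean window = 30 + [1 - exp(-μ(F-30))]/μ: 9.2 months against 6.5, a ratio of 1.4. Calendar follow-up alone would suggest about 4 (42/10).

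**3. Other event types and follow-up lengths (175-day median)**

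| Event | F = 42 mo | F = 10 mo |
|---|---|---|
| 5% risk per 6 months | 7.4% | 5.4% |
| 10% | 14.2% | 10.6% |
| 20% | 26.3% | 20.8% |
| 50% | 54.4% | 49.2% |
| 10%, onset only after month 6 | 6.9% | 2.9% |
| Confined to cycle 1 | no difference | no difference |

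For the 10% event, F = 20 months gives 13.3%, so the gap from 14.2% is already small. F = 4 months, possible only at an interim, gives 6.0%.

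**4. Sensitivity to time on treatment (10% event)**
- Median 130 days in both groups: 11.3% against 9.4%.
- Median 230 days in both groups: 17.3% against 11.6%.
- Median 130 days on FMI I (F = 42) and 230 days on FMI III: 11.3% against 11.6% (F = 10) or 15.5% (F = 20). The direction reverses.

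**5. What the alternatives give under the same truth**
- Exposure-adjusted rate: λ × 365.25 × 100 = 21.1 per 100 patient-years, or 21.1/12 = 1.76 per 100 patient-months, in both groups whatever F is.
- Common window of 6 cycles (168 days): 0.0172 + 0.9828 × 0.1271 × [1 - exp(-0.00454 × 138)] = 0.0172 + 0.9828 × 0.1271 × 0.465 = 7.5% in both groups, because 168 days lies inside the 10-month floor.

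**The case against.** The other side has several sound points.

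- **Formulation safety is already compared on a fixed window.** Protocol 2.3 and SAP 2.9 describe a review of the first 20 FMI III patients to the end of cycle 1 against FMI I, and SAP 1.1 plans the same for FMI IV against FMI III. No formulation hypothesis or test is attached to the TEAE tables. This stands, but these reviews stop at one cycle and the first covers only 20 FMI III patients.
- **The Sensitivity Analysis Set (SAP 2.2.4) limits the second-interim problem.** It leaves out late entrants who are still on treatment without progression, and some key safety analyses are repeated on it. It does not address the primary analysis.
- **Treatment normally stops at progression**, so observation differs far less than calendar time does. This is why the window ratio is about 1.4 and why 14.2% against 10.6% is an upper-end contrast at that median: many FMI III patients have more than 10 months.
- **Exposure duration is reported by formulation**, so a careful reader can see unequal observation, though not correct for it.
- **Adjustment does not make the contrast causal.** Formulation is confounded with era, and patients who switch to FMI IV keep their first label. This stands, and the fix should say so.

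A reader might also infer that FMI III patients have 10 months or less. At the primary analysis 10 months is the minimum; less is possible only at the interims, for late-dosed patients.

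**Conclusion.** The point holds for Cohort 1, FMI I against FMI III. The planned TEAE, SAE and AESI percentages can differ between formulations when the underlying hazards do not, and nothing planned for the primary analysis corrects this beyond cycle 1. For an event with 10% risk per 6 months, the upper-end gap is 3.6 percentage points (14.2 - 10.6) with a 175-day median time on treatment; it is 1.9 points at 130 days and 5.7 at 230 days. It shrinks quickly as FMI III follow-up passes 10 months, is proportionally largest for late-onset events, and vanishes for cycle-1 events. These sizes rest on exponential time on treatment, PFS as its proxy, and illustrative constant hazards.

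Three stronger readings are not supported:
- That newer formulations will look safer. The direction depends on time on treatment by formulation, which the documents do not give, and it can reverse.
- That FMI IV is affected in the same comparison. Patients who start on FMI IV are in Cohorts 2 and 3, which are analysed separately.
- That the FGFR-status split is biased in a known direction. All 14 non-fusion patients come from the pre-Amendment 2 era, their exposure is not given, and the second interim includes only fusion patients.

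This is a worthwhile, inexpensive improvement. It does not invalidate the overall safety tables.

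**What to change.** In SAP 2.7.2.1.2, for the Cohort 1 by-formulation overview, SAE and AESI tables:

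1. Add the cumulative incidence of first onset within a common window, for example the first 6 cycles, with censoring at data cutoff. State how the end of the on-treatment period without an event is handled, for example as a competing event.
2. Add exposure-adjusted incidence: patients with a first event per 100 patient-months at risk.
3. State that crude percentages are not to be used to compare formulations, and that any such comparison is descriptive because formulation is non-randomised and assigned by the first one received.

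Keep the crude percentages for the overall column. The dose and event dates needed are already collected, so the cost is SAP wording and more table output. The person-time rate assumes a roughly constant hazard, which is why the common-window estimate should accompany it.

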2.7.2.2.1 CTC Grading for Laboratory Parameters

Grade categorization of lab values will be assigned programmatically as per NCI Common Terminology Criteria for Adverse Events (CTCAE) version 4.03. The calculation of laboratory CTC grades will be based on the observed laboratory values only; clinical assessments will not be taken into account.

For laboratory tests where grades are not defined by CTCAE v4.03, results will be graded by the low/normal/high (or other project-specific ranges, if more suitable) classifications based on laboratory normal ranges.

A severity grade of 0 will be assigned for all non-missing lab values not graded as 1 or higher for CTCAE parameters that are unidirectional. For CTCAE parameters that are bidirectional non-gradable values which are beyond the normal range will be left missing while Grade 0 will be assigned to the value within the normal range. Grade 5 is not applicable.

